## **All Treated Patients Analysis Set**

The All Treated Patients analysis set includes all patients who receive any amount of brentuximab vedotin or nivolumab. The All Treated Patients set will be used for presentation of safety data and may be used for exploratory analyses of efficacy endpoints.

## **Efficacy Evaluable Analysis Set**

The Efficacy Evaluable analysis set includes all patients who had an adequate baseline disease assessment, received any amount of either drug, and subsequently had an adequate response assessment. The Efficacy Evaluable set will be used for exploratory analysis of efficacy endpoints.

### **9.3.1.8 Examination of Subgroups**

As exploratory analyses, subgroup analyses may be conducted for selected endpoints. Detailed methodology will be provided in the SAP.

### **9.3.1.9 Timing of Analyses**

Analysis of the primary endpoint will be carried out after all patients have had their EOT assessments. Interim summaries of various endpoints may be presented at scientific congresses prior to the final analysis of the primary endpoint. Interim summaries will also be presented to the SMC. Database cutoff will be determined after all patients have completed treatment.

## **9.3.2 Patient Disposition**

An accounting of study patients by disposition will be tabulated and the number of patients in each analysis set will be summarized. Patients who discontinue study treatment and patients who withdraw from the study will be summarized with reason for discontinuation or withdrawal.

## **9.3.3 Patient Characteristics**

Demographics and other baseline characteristics will be summarized. Details will be provided in the SAP.

## **9.3.4 Treatment Compliance**

The dose administered at each cycle for each treatment agent will be assessed and dose intensity will be summarized. Details will be provided in the SAP.

## **9.3.5 Efficacy Analyses**

### **9.3.5.1 Primary Efficacy Analyses**

CR rate at the EOT visit will be calculated using the All Enrolled Patients analysis set and will include all patients in this analysis set who were enrolled on the dose regimen chosen for Part 2. A two-sided 90% exact binomial CI will be calculated ([Clopper 1934](#)) and the test will be carried out for the following null and alternative hypotheses:

- $H_0$ : CR rate  $\leq 30\%$
- $H_1$ : CR rate  $> 30\%$

The test will be carried out using a one-sided exact binomial test at level  $\alpha=0.05$ , thus the null will be rejected in favor of the alternative if  $P < 0.05$  is observed.

### 9.3.5.2 Secondary Efficacy Analyses

ORR at EOT will be calculated using the All Enrolled Patients set and its two-sided 95% exact binomial CI will be presented ([Clopper 1934](#)). Additional summaries of ORR may be presented based on patient demographics of interest. Summaries may also be presented using the All Treated Patients and the Efficacy Evaluable analysis sets. PFS and duration of response estimates will be based on Kaplan-Meier methodology and Kaplan-Meier plots will be presented. The median PFS and duration of response times will be determined and their two-sided 95% CI calculated using the log-log transformation method ([Collett 1994](#)).

### 9.3.5.3 Additional Efficacy Analyses

OS and PFS estimates will be based on Kaplan-Meier methodology and Kaplan-Meier plots will be presented. The median OS time will be determined and its two-sided 95% CI calculated using the log-log transformation method ([Collett 1994](#)).

## 9.3.6 Pharmacokinetic and ATA Analyses

Pharmacokinetic parameters to be estimated for brentuximab vedotin and MMAE include the area under the concentration-time curve (AUC), maximum concentration ( $C_{\max}$ ) or concentration at the end of infusion ( $C_{\text{eoI}}$ ), the time  $C_{\max}$  occurred ( $T_{\max}$ ), and trough concentration ( $C_{\text{trough}}$ ) for brentuximab vedotin. For nivolumab,  $C_{\text{eoI}}$  and  $C_{\text{trough}}$  will be summarized. The incidence of ATA to brentuximab vedotin and to nivolumab will also be assessed.

## 9.3.7 Biomarker Analyses

Relationships of biomarkers (e.g., baseline values, absolute and relative changes from baseline) to efficacy, safety and PK parameters will be explored. Relationships and associated data that are determined to be of interest will be summarized. Details will be described separately.

## 9.3.8 Safety Analyses

### 9.3.8.1 Extent of Exposure

Exposure for each treatment agent, including duration of treatment, number of cycles, total dose, dose modifications, and dose intensity will be summarized using the All Treated Patients analysis set.

Details will be provided in the SAP.

### **9.3.8.2 Adverse Events**

Adverse events will be defined as treatment emergent if they are newly occurring or worsen following treatment with either brentuximab vedotin or nivolumab. The incidence of all AEs, treatment-emergent AEs, and treatment-related AEs will be tabulated. AEs will be classified by system organ class and preferred term using the Medical Dictionary for Regulatory Activities (MedDRA).

AEs will be listed and summarized by MedDRA preferred term, severity, and relationship to study drug. In the event of multiple occurrences of the same AE with the same preferred term in one patient, the AE will be counted once as the occurrence. The incidence of AEs will be tabulated by preferred term and treatment group. AEs leading to premature discontinuation of study drug will be summarized and listed in the same manner.

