#### **Diagnosis versus Signs or Symptoms**

In general, the use of a unifying diagnosis is preferred to the listing out of individual symptoms. Grouping of symptoms into a diagnosis should only be done if each component sign and/or symptom is a medically confirmed component of a diagnosis as evidenced by

standard medical textbooks. If any aspect of a sign or symptom does not fit into a classic pattern of the diagnosis, report the individual symptom as a separate AE.

Adverse reactions associated with the infusion of study drugs must be recorded as both the NCI CTCAE term for infusion-related reaction (e.g., cytokine release syndrome, acute infusion reaction, or allergic or hypersensitivity reaction) and with each sign or symptom recorded as an individual adverse event. Level of severity for both the overall infusion-related reaction term and the individual signs and symptoms should also be recorded.

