7.6.1 Adverse Events

Adverse events (AEs) will be listed and summarized by MedDRA preferred term, severity, and relationship to study drug in descending frequency unless otherwise specified. The incidence of all AEs, treatment-emergent AEs, and treatment-related AEs will be tabulated. For incidence reporting, if a patient reports more than one AE that was coded to the same system organ class or preferred term, the patient will be counted only once for that specific system organ class or preferred term.

A treatment-emergent AE is defined as a newly occurring or worsening AE after the first dose of brentuximab vedotin or nivolumab. The incidence of AEs will be tabulated by preferred term and presented by dose regimen and overall. Summaries will also be presented for AEs occurring prior to start of ASCT and on or after start of ASCT, where start of ASCT is defined as the start date of conditioning regimen for ASCT. Summaries of AEs will also be provided dose regimen and overall for the following:

- Pre-existing Adverse Events
- All treatment-emergent AEs
- AEs related to brentuximab vedotin
- AEs related to nivolumab
- Serious Adverse Events (SAEs)
- SAEs related to brentuximab vedotin
- SAEs related to nivolumab
- AEs leading to dose delay of brentuximab vedotin or/and nivolumab
- AEs leading to dose reduction of brentuximab vedotin or/and nivolumab
- AEs leading to dose interruption (full dose received) of brentuximab vedotin or/and nivolumab

- AEs leading to dose elimination of brentuximab vedotin or/and nivolumab
- AEs leading to treatment discontinuation
- AEs that started during infusion,
- AEs that started within 24 hours post infusion,
- Treatment-emergent AEs by system organ class, preferred term and maximum severity; at each system organ class or preferred term, multiple occurrences of events within a patient are counted only once at the highest severity
- Grade 3 5 treatment-emergent AEs
- Treatment-emergent AEs by system organ class and preferred term
- AEs of peripheral neuropathy identified by the broad search MedDRA SMQ "peripheral neuropathy"
- Infusion related reactions due to brentuximab vedotin, or/and nivolumab
- Onset of infusion reactions related to brentuximab vedotin, or/and nivolumab by preferred term by cycle

Listings will be presented for all adverse events, serious adverse events, adverse events leading to treatment discontinuation, and adverse events leading to death.

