APPENDIX B: DEFINITION OF THE TERM "TREATMENT-EMERGENT" WITH RESPECT TO AE CLASSIFICATION

The algorithm below should be used to determine whether an adverse event (AE) is classified as a treatment-emergent adverse event (TEAE). A TEAE is defined as any AE which is newly occurring or worsening in severity, where newly occurring means that the AE was not present at baseline. For ease of reading, both pre-existing conditions and AEs will be referred to as AEs for the remainder of this document. AE dates should be imputed in accordance with the algorithm detailed in Appendix A. prior to determination of TEAE classification. Details of the TEAE classification are as follows:

- 1) Determine the first/earliest dose date of any study treatment (for combination studies this includes any component of the regimen)
- 2) **Baseline AEs:** classify an AE as a baseline AE if it satisfies both of criteria 1 and 2 below:
 - 1. The onset period field is: "started before the signing of informed consent"; or "started after consent but before the first dose of any study treatment"; or, the onset period field is missing and the AE start date is prior to the first dose date of any study drug (step 1, above).
 - 2. The stop date satisfies either of i or ii below:
 - i. The stop date is the same as or a later date than the first dose date of any study treatment
 - ii. The stop date is missing with outcome equal to
 - recovering/resolving (this outcome may or may not be associated with a date),
 or
 - not recovered/not resolved, or
 - unknown.
 - Note: if the AE has no outcome or stop date provided, the CRF data should be queried

Note: If the event ended on Day 1 (the date of first dose of any study drug) it will be considered a baseline event.

- 3) **Post-baseline AEs:** classify an AE as post-baseline if it meets either of criteria 1 or 2 below:
 - 1. The onset period of the AE is "started after the first dose of any study treatment"
 - 2. The onset period of the AE is missing and the AE start date is the same as or a later date than the first dose date of any study treatment
- 4) Compare post-baseline AEs to baseline AEs using the lower level term (LLT) and determine classification. Note that classification may not be possible and the TEAE variable will be missing:
 - 1. Classify all baseline AEs as not treatment emergent (not TEAEs).

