 - 2. If a baseline and post-baseline AE have the same LLT but the post-baseline AE has a greater CTC grade then classify the post-baseline AE as a TEAE. If the post-baseline

- grade is less than or equal to the baseline grade then the post-baseline AE is not a TEAE.
- 3. If there are no baseline AEs with a matching LLT for the post-baseline AE then classify the post-baseline AE as a TEAE.
- 4. If the post-baseline AE is uncoded then classify the post-baseline AE as a TEAE.

NOTE:

For summaries which include only treatment emergent AEs include all AEs which are classified as TEAEs as well as those AEs for which TEAE status could not be determined (e.g., the value of the TEAE variable may be missing if the event cannot be identified as baseline or post-baseline - missing information on the AE CRF should be queried). Only exclude those AEs which were determined to not be treatment emergent.

Events that have an end date prior to the first dose date (e.g. protocol procedure related events) should be classified as not treatment emergent (not TEAEs).

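### SAP Appendix B keeps out of the treatment-emergent tables a new same-or-lower-grade episode of an event that was present on Day 1 and has since resolved

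*Protocol*

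**What the plan says.** The two general definitions agree. Protocol Section 9.3.8.2: "Adverse events will be defined as treatment emergent if they are newly occurring or worsen following treatment with either brentuximab vedotin or nivolumab". SAP Section 7.6.1: "A treatment-emergent AE is defined as a newly occurring or worsening AE after the first dose of brentuximab vedotin or nivolumab". Neither explains what newly occurring means for a condition that was present, went away and came back.

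SAP Appendix B supplies the operating rule:

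- It narrows the term: "where newly occurring means that the AE was not present at baseline".
- A baseline AE is one that began before the first dose and meets a stop-date condition: "The stop date is the same as or a later date than the first dose date of any study treatment". The alternative is a missing stop date with an unresolved or unknown outcome. A note adds: "If the event ended on Day 1 (the date of first dose of any study drug) it will be considered a baseline event".
- Step 4 matches post-baseline to baseline AEs by LLT. A matching post-baseline AE of higher grade is a TEAE. If its "grade is less than or equal to the baseline grade then the post-baseline AE is not a" TEAE.

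Step 4 does not ask whether the baseline event had ended before the post-baseline one began. SAP Section 9.1 reports no changes from the protocol.

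**The concern.** The protocol collects what is needed to see a recurrence. Section 7.6.1.1 has sites record every condition present before dosing on Day 1, and later changes in its severity, frequency or character. Appendix B then discards part of this when it assigns treatment-emergent status. A low-grade symptom that is present on Day 1 and clears a few days later removes every later same-grade episode of that LLT from the TEAE count, however long the gap.

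The terms exposed are those that can be both disease symptoms and drug effects. B symptoms are assessed on Cycle 1 Day 1. Protocol Section 5.6.1 lists fever, rash, itching and joint pain among the signs of infusion reactions. Neuropathy is exposed too: exclusion criterion 12 bars only Grade 2 or higher, so patients may enter with Grade 1. Under SAP Section 7.6.1.1, treatment-emergent status decides who enters the neuropathy incidence, time-to-onset and outcome-category summaries. At stake is whether TEAE rates for such terms are read as complete when they can only err low from this cause.

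**Working it through.** **The nearest figure in the plan.** No stated figure depends on this rule. The only safety calculation (Protocol Section 9.1, SAP Section 6.2) is the chance of seeing at least one AE of true rate 5% in 55 patients: 1 − 0.95^55 = 0.9405. This reproduces the stated 94%. It refers to AEs in general, so it is not itself wrong.

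**Appendix B applied literally.** Day 1 is the first dose. Each case has a baseline event with onset before Day 1, then a separate post-baseline event with the same LLT on Day 30. The last column assumes that each ended baseline event has a recovered/resolved outcome.

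| Baseline event | New event | Appendix B now | With the fix below |
|---|---|---|---|
| Grade 1, ended Day −3 | Grade 1 | TEAE (not a baseline AE) | TEAE |
| Grade 1, ended Day 1 | Grade 1 | not a TEAE | TEAE |
| Grade 1, ended Day 10 | Grade 1 | not a TEAE | TEAE |
| Grade 2, ended Day 10 | Grade 1 | not a TEAE | TEAE |
| Grade 1, ended Day 10 | Grade 2 | TEAE | TEAE |
| Grade 1, ongoing | Grade 1 | not a TEAE | not a TEAE |

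Rows 2 to 4 are the problem. Row 1 marks its limit: only events still present on Day 1 block later ones.

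**Duration of the block.** Step 4 sets no time limit. With four 21-day cycles the Day 1 doses fall on Days 1, 22, 43 and 64. Reporting runs to 100 days after the last nivolumab dose, so on schedule to 64 + 100 = Day 164.

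**Why a stop date cannot be the trigger for a fix.** In Appendix A, Example 1, one unresolved headache is entered as successive severity records. The first dose is 01JAN2012. The baseline Grade 1 record ends on 15APR2012 with outcome not recovered/resolved. Later records rise to Grade 2 and Grade 3, and Grade 1 records start on 31MAY2012 and 10JUL2012. If any record starting after the baseline stop date counted, both Grade 1 records would become TEAEs although the headache never resolved. A rule tied to a resolved outcome leaves them as they are now.

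**Size.** The documents give no baseline symptom rates and no recurrence rates. Let T be the true on-treatment incidence of a term. Let s be the share of those patients with a matching baseline event at the same or a higher grade that resolved on or after Day 1. The table then shows at least T × (1 − s). This is a floor on the displayed rate, because a patient leaves the row only if every on-treatment episode is blocked. Purely as an assumption, take T = 14/55 = 25.5%:

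- s = 10%: 25.5% × 0.9 = 22.9%
- s = 20%: 25.5% × 0.8 = 20.4%
- s = 40%: 25.5% × 0.6 = 15.3%

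The same assumed shares, applied in full to a 5% event in 55 patients, lower the chance of at least one visible TEAE from 94.0% to:

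- s = 10%: 1 − 0.955^55 = 92.1%
- s = 20%: 1 − 0.96^55 = 89.4%
- s = 40%: 1 − 0.97^55 = 81.3%

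**The case against.** The case for leaving the rule alone has real substance.

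- **It is a stated convention.** The protocol leaves newly occurring undefined, and Section 9.3 defers detail to the SAP. A reader might infer that Appendix B contradicts the protocol. The documents support only a narrowing that is not flagged.
- **The episodes remain elsewhere.** A reader might infer that they vanish from the primary safety output. They do not: the primary endpoint is AEs, not TEAEs, and SAP Section 7.6.1 also plans all-AE incidence, AEs starting during or within 24 hours of infusion, infusion-reaction summaries and full listings. The SAP does not say whether the drug-related and serious AE summaries are limited to TEAEs.
- **Infusion reactions are largely protected.** Protocol Section 7.6.1.2 requires the reaction term itself as well as its components, "with each sign or symptom recorded as an individual adverse event". A baseline fever would not match the LLT of the reaction term.
- **LLT matching works the other way.** A stable baseline condition recoded to another LLT would count as new, which adds TEAEs. A reader might want preferred-term matching as part of the remedy. That is an optional convention, and alone it would widen the block.

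All four limits stand, but they do not remove the gap. The all-AE table counts a patient once per preferred term. If it includes pre-existing conditions, as Appendices A and B do when they call both AEs, a patient with baseline fever only looks the same as one with baseline fever and a new on-treatment episode. Listings show the episode but give no incidence.

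**Conclusion.** The concern holds in a limited form. An event present on Day 1 that resolves on or after Day 1 blocks any later separate episode of the same LLT at the same or a lower grade from being a TEAE. For that patient group the rule is narrower than Protocol Section 9.3.8.2 and SAP Section 7.6.1, and SAP Section 9.1 does not say so. By itself the rule can only lower TEAE counts. It bears mainly on low-grade terms, because a Grade 3 or higher event is lost only if the baseline grade was at least as high. Treatment-emergent neuropathy incidence, onset and outcome categories are the clearest summaries affected.

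It should not be read as reaching events that ended before the first dose; Appendix B does not treat those as baseline AEs. Nor should the percentages above be read as the loss. They rest on an assumed incidence and assumed shares, and they bound the effect from above, since one higher-grade or differently coded episode keeps the patient in the row. The true size cannot be derived from the documents. The correction is worth making because it is cheap, not because a large bias has been shown.

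**What to change.** Amend SAP Appendix B step 4 as follows:

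- Apply the exclusion for grades at or below the baseline grade only until the baseline condition has an outcome of recovered/resolved or recovered/resolved with sequelae.
- Classify a separate event that starts after that resolution as a TEAE, whatever its grade.
- Keep successive severity records of one unresolved condition, as in Appendix A Example 1, under the existing grade comparison.

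The program should take the outcome from the last chronological record of the condition. In Appendix A Example 2 the baseline nausea record is not recovered/resolved, and only the final record carries the resolved outcome.

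The cost is SAP wording and a small change to the TEAE program, using outcome and date fields already collected. Site conduct does not change, so under Protocol Section 9.3 no protocol amendment is needed. The downside is small: some disease-related recurrences will count, and a few TEAE rates will rise slightly. Changing from LLT to preferred-term matching is not required.

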### **9.3.8.3 Deaths and Serious Adverse Events**

Serious adverse events will be listed and summarized in the same manner as all AEs. Events with a fatal outcome will be listed.

### **9.3.8.4 Clinical Laboratory Results**

Summary statistics for actual values and for change from baseline may be tabulated as appropriate for laboratory results and scheduled visit. Laboratory values will be listed with grade per NCI CTCAE and out of normal reference range flags.

### **9.3.9 Interim Analyses**

In Part 1 of the study, an SMC will monitor the trial for safety and provide guidance regarding possible enrollment of additional patients in Part 1 and possible expansion of enrollment in Part 2. Initially 6 patients will be enrolled in Part 1. If a patient discontinues treatment for reasons other than a DLT prior to 6 patients completing the DLT evaluation period then they will be replaced (as long as the arm remains open). These patients will be monitored for DLT throughout the DLT evaluation period (see Section 3.1.4 for details regarding the definition of DLT and DLT-evaluable). The SMC will review safety data and provide recommendations when either of the following occurs:

1. 2 or more of the patients in the current arm are determined to have had a DLT based on the protocol definition.
2. 6 patients complete the DLT evaluation period (by either remaining on treatment or having a DLT).

On review of all available data, the SMC may determine that the classification of DLT was not appropriate for one or more of the patients, in which case enrollment may resume if the target of 6 patients has not yet been reached. However, if 2 or more patients were determined to have experienced DLT, then expansion will not occur as the next step. Based on SMC recommendations, additional patients may be enrolled at modified treatment and/or dosing levels (details in Section 3.1). These additional patients will then be assessed for DLT in the same manner described above to determine if it is appropriate to expand

enrollment. If it is determined by the SMC that due to safety concerns no additional dose levels or schedules should be enrolled, then the study will be closed to enrollment.

Additionally, interim data from the study may be presented at scientific meetings such as the annual meetings of the American Society of Clinical Oncology and the American Society of Hematology.

